9.1.2 Secondary Outcome(s)

- Mean change in systolic and diastolic blood pressure from baseline to 6 weeks and 12 weeks
- Prevalence of falls between placebo and active group
- Prevalence of intolerable side effects between placebo and active group
- Prevalence of study discontinuation between placebo and active group
- Differences in overall compliance between placebo and active group

9.1.3 Exploratory Outcome(s)

- Difference in ATP levels in red blood cells and brain within subjects before and after taking study drug on day 1
- Difference in ATP levels in red blood cells and brain within subjects at 6 and 12 weeks compared to baseline reading
- Difference in ATP levels in red blood cells and brain between groups at 6 weeks and 12 weeks
- Slope of change over 12 weeks of the MDS-UPDRS Part 1
- Slope of change over 12 weeks of the MDS-UPDRS Part 2
- Slope of change over 12 weeks of the MDS-UPDRS Part 3 (OFF)
- Slope of change over 12 weeks of the MDS-UPDRS Part 4 (OFF)
- Absolute change over 12 weeks of the MDS-UPDRS Parts 1, 2, 3, 4, and TMS (OFF)

FAST TZ-PD

Version 2.0

Version date: 11/12/2019

- Slope of change over 12 weeks of MDS-UPDRS TMS (OFF) (direct comparison for efficacy)
- Slope of change over 12 weeks of the Hoehn & Yahr Score
- Slope of change over 12 weeks of all cognitive assessments between placebo and active group
- Slope of change over 12 weeks of sleep assessments between placebo and active group
- Slope of change over 12 weeks of behavioral assessments between placebo and active group

9.2 Sample Size and Accrual

This is a pilot study and the sample size was chosen based on available funding and resources

9.3 Data Monitoring

All aspects of the study will be monitored by the PI of the study. Monitoring will be conducted according to Good Clinical Practice and applicable government regulations. The investigator agrees to allow monitors access to the clinical supplies, dispensing and storage areas, and to the clinical files of the study subjects, and, if requested, agrees to assist the monitors.

An adverse event (AE) is any unfavorable and unintended sign (including a clinically significant abnormal laboratory finding, for example), symptom, or disease temporally associated with a study, use of a drug product or device whether or not considered related to the drug product or device. FDA and Office of Human Research Protection (OHRP) requirements for reporting AEs will be followed. Subjects will be monitored for AEs from the time they sign consent until 30 days following permanent discontinuation of study drug. At that point, all ongoing AEs will be followed to resolution, but no new AEs will be recorded.

The PI and research team (co-Investigators, research nurse, clinical trial coordinator) are responsible for identifying and reporting AEs and determining the relationship of the event to the study drug/study procedures.

9.4 Data Analyses

The following outcome measures will be analyzed under an intention-to-treat protocol. All randomized individuals will be included regardless of their final treatment status.

- Primary Outcome
 - Rate of drop out between groups
 - Chi-square
 - Rate of adverse events between groups
 - Chi-square
- Secondary outcomes
 - Prevalence of orthostatic hypotension between placebo and active group
 - Chi-square
 - Prevalence of falls between placebo and active group
 - Chi-square
 - Differences in overall compliance between placebo and active group
 - Linear mixed effect models that includes compliance at each study visit for each participant
- Exploratory outcomes
 - Difference in ATP levels in red blood cells and brain within subjects before and after taking study drug on day 1
 - Paired samples t-test
 - Difference in ATP levels in red blood cells and brain within subjects at 6 and 12 weeks compared to baseline reading

- Paired samples t-test
- Difference in ATP levels in red blood cells and brain between groups at 6 weeks and 12 weeks
 - Independent samples t-test
- Slope of change over 12 weeks of the MDS-UPDRS Part 1
 - LMER
- Slope of change over 12 weeks of the MDS-UPDRS Part 2
 - LMER
- Slope of change over 12 weeks of the MDS-UPDRS Part 3
 - LMER
- Slope of change over 12 weeks of the MDS-UPDRS Part 4
 - LMER
- Absolute change over 12 weeks of the MDS-UPDRS Parts 1, 2, 3, 4, and TMS
 - Independent samples t-tests
- Slope of change over 12 weeks of MDS-UPDRS TMS (direct comparison for efficacy)
 - LMER
- Slope of change over 12 weeks of the Hoehn & Yahr Score
 - LMER
- Slope of change over 12 weeks of all cognitive assessments between placebo and active group
 - LMER
- Slope of change over 12 weeks of sleep assessments between placebo and active group
 - LMER
- Slope of change over 12 weeks of behavioral assessments between placebo and active group
 - LMER

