We will randomize 20 PD patients to receive TZ or placebo. Ten of the participants will be randomized to receive TZ 5mg daily for 12 weeks and 10 participants will be randomized to receive a daily placebo for 12 weeks. This aim will generate data on safety and tolerability of TZ in a population of patients with PD. As an exploratory outcome, we aim to determine if treatment with TZ in patients with PD improves markers of energy metabolism. Furthermore, we will determine if cellular and cerebral ATP levels correlate with disease severity and progression. Participants will also participate in an assessment that will include, but is not limited to a motor exam, a neuropsychological assessment, and functional assessments. Clinical findings will be used to guide future clinical trials.

Interventions and Duration

Participants in this study will be randomized to receive either TZ 5 mg by mouth once daily or a matched placebo once daily. Once randomized, each participant will receive their assigned treatment for 12 weeks. Participants will be assessed via telephone for 3 weeks after their 2 week visit, then 6 weeks months after their baseline visit, then via telephone 9 weeks after their baseline visit, and their last visit will occur 12 weeks from their baseline visit. We anticipate that this study can be completed (study open to end of data analyses) within 9 months.

Sample Size and Population

This study will randomize 20 participants: 10 participants will be randomized to receive 5mg of TZ daily and 10 participants will be randomized to the placebo group. It is anticipated that no more than 35 participants will need to be screened to enroll these participants.

This study will include participants who are ≥ 40 years old who have a confirmed diagnosis of PD made by a neurologist and a Hoehn & Yahr score at baseline of < 4 . Participants will be excluded from this study if any of the following are true:

- Participants has orthostatic hypotension or a sitting blood pressure of $\leq 90/60$
- Participant is pregnant
- Participant has a deep brain stimulation device implanted
- Participant has a known allergy or sensitivity to terazosin
- Participant is concomitantly taking doxazosin, alfuzosin, prazosin, urapadil, or tamsulosin
- Participant has active drug or alcohol use or dependence that, in the opinion of the site investigator, would interfere with adherence to study requirements
- Participant is unable or unwilling to give written informed consent

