4.4 Subject Withdrawal Criteria

Subjects are free to withdraw from the study at any point. Subjects will be withdrawn from the study if they experience serious and/or persistent side effects during the study that, in the opinion of the site PI, are thought to be related to the study drug. Examples include but are not limited to persistent and symptomatic orthostatic hypotension, persistent peripheral edema, persistent drowsiness that significantly affects activities of daily living, significant weakness, or falls. If any of these side effects occur, the site PI will be asked to make a recommendation regarding whether continuation of the study treatment will place the subject at any undue risk. If so, the subject will be immediately withdrawn from the study.

Withdrawn subjects will not be replaced. Should a subject withdraw from the study despite all efforts to maintain follow-up every effort should be made to obtain an in-person final visit, which should include all assessments that would be obtained in the final drug visits (see Section 6).

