5.3.2 Prohibited Medications/Interventions

Subjects are prohibited from taking doxazosin, alfuzosin, prazosin, terazosin, urapadil, or tamsulosin during this study. If one of these medications is prescribed during the course of the study, the participant will be informed that initiation of any of these treatments will result in their immediate withdrawal from the study. They may decide if they wish to receive the prescribed treatment from their outside provider. If the subject decides to not initiate the prohibited treatment, they may remain in the study.

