6.2.3 Study Medication Discontinuation Evaluations/procedures

Study medication discontinuation will occur under the following circumstances:

- Completion of study
- Presence of orthostatic hypotension
- Blood pressure of ≤90/60
- Participant initiates prohibited medication
- Participant reports unwillingness to continue with study due to intolerable side effects

If any of the above occurs, participants will be asked to come in for an end-of-study visit as soon as possible. All assessments outlined in the SoA will be performed at the end-of-study visit. Participants will not be required to continue for future follow-up appointments after discontinuation of treatment. Participants who experience adverse effects will immediately discontinue study treatment and will not be considered for inclusion in further evaluations.

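### Falls are compared as a yes/no proportion over all randomized participants, but the protocol contradicts itself on falls follow-up after drug is stopped and gives no rule for incomplete observation

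*Combined protocol and SAP*

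**What the plan says.** Section 9.4 sets one analysis population for every outcome: "All randomized individuals will be included regardless of their final treatment status". Among the secondary outcomes it lists "Prevalence of falls between placebo and active group", with chi-square as the method. It gives no person-time, no missing-data method, and no rule for scoring a participant whose falls observation stops before week 12.

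The trial is small. The synopsis says "This study will randomize 20 participants: 10 participants will be randomized to receive 5mg of TZ daily and 10 participants will be randomized" to placebo, and 9.2 explains that "This is a pilot study and the sample size was chosen based on available funding and resources". No fall rate or drop-out rate is given. Follow-up is 12 weeks ("their last visit will occur 12 weeks from their baseline visit"), and the Schedule of Activities in 6.1 asks about recent falls at weeks 2, 3, 4, 5, 6, 9 and 12.

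On observation after drug is stopped, the protocol says several things:

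- **6.2.3** requests an end-of-study visit with the scheduled assessments, then says: "Participants will not be required to continue for future follow-up appointments after discontinuation of treatment". It adds that people with adverse effects are left out of further evaluations.
- **6.2.4** declares an intention-to-treat design, asks those who stop drug to stay in follow-up until the study ends, and lists fall assessments among the off-drug assessments.
- **Section 8** encourages them to complete all remaining assessments.
- **4.4** covers side effects that the site PI judges to carry undue risk: "If so, the subject will be immediately withdrawn from the study". It also asks for a final in-person visit.
- **5.3.2** says of the prohibited drugs that "initiation of any of these treatments will result in their immediate withdrawal from the study".
- **9.3** keeps adverse event monitoring open for 30 days after permanent discontinuation.

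**The concern.** A yes/no comparison with a fixed denominator of ten per arm needs a value for every participant. If the site follows 6.2.3, someone who stops at week 2 without a fall supplies two weeks of data to a twelve-week proportion. With no scoring rule, the absence of a recorded fall can easily be entered as no fall.

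The loss may not be neutral. The discontinuation triggers in 6.2.3 and section 8 include orthostatic hypotension, low blood pressure and intolerable side effects. Section 2.3 associates TZ with orthostatic hypotension, says that orthostatic hypotension could make falls worse, and says the study will assess both directly. So the people whose observation is cut short may be the ones more likely to fall, and there may be more of them on TZ. What is at stake is a descriptive safety estimate that section 3.1 hopes will guide later trials.

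**Working it through.** The plan has no fall or drop-out figure to reproduce, so the rates below are assumptions.

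**Step 1. The follow-up rules side by side.** Take a participant who stops drug at week 2 for a side effect. Under 6.2.3 there is an end-of-study visit and nothing further. Under 6.2.4 follow-up continues to the end of the study, with falls assessed at off-drug visits; the telephone calls are not mentioned. Under section 8 all remaining assessments are encouraged, which would include the falls questions at the calls in weeks 3, 4, 5 and 9. These cannot all be applied, and 9.4 does not say which data it expects.

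**Step 2. Size of the possible bias.** Let p be the 12-week fall risk with full observation, d the fraction of an arm that stops, and w the week at which falls data end. Assume a constant fall hazard, and score leavers with no recorded fall as fall-free.

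- Fall risk by week w: r(w) = 1 − (1 − p)^(w/12)
- Raw prevalence over all randomized: (1 − d)·p + d·r(w)
- With equal p and w in both arms, the bias in TZ minus placebo is −(d_TZ − d_placebo)·(p − r(w))

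The last line shows that equal loss, timing and risk give zero bias between arms, although both prevalences are too low.

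Take p = 30%, d_placebo = 10% and d_TZ = 20% to 40%. For stops at week 2, r(2) = 1 − 0.7^(2/12) = 5.8%, and the bias runs from −0.1 × (30 − 5.8) to −0.3 × (30 − 5.8) points. If the adverse event window captures every fall for 30 days (30/7 = 4.29 weeks), replace w by w + 4.29.

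| Stop | Falls data end | r(w) | p − r(w) | Bias, d_TZ 20% | Bias, d_TZ 40% |
|---|---|---|---|---|---|
| Week 2 | at stop | 5.8% | 24.2 | −2.4 points | −7.3 points |
| Week 2 | 30 days later | 17.0% | 13.0 | −1.3 points | −3.9 points |
| Week 6 | at stop | 16.3% | 13.7 | −1.4 points | −4.1 points |
| Week 6 | 30 days later | 26.3% | 3.7 | −0.4 points | −1.1 points |

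Varying p from 20% to 50%, without the window, widens the range to −0.9 to −11.7 points.

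**Step 3. How much the missing rule matters for one data set.** Suppose TZ has 3 fallers, 3 leavers with no recorded fall and 4 completers without a fall, and placebo has 2 fallers in 10.

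| Rule for the 3 leavers | TZ prevalence | Chi-square p | Fisher p |
|---|---|---|---|
| Fall-free | 3/10 = 30% | 0.61 | 1.00 |
| Omitted | 3/7 = 43% | 0.31 | 0.59 |
| Fallers | 6/10 = 60% | 0.07 | 0.17 |

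Omitting them conflicts with the all-randomized rule in 9.4.

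**Step 4. Does person-time alone cure it?** Take three of ten TZ participants leaving at week 2 with twice the hazard of the others, and set the others' and the placebo hazard to 1. Stayers give 7 × 12 = 84 person-weeks. Leavers give 3 × 2 = 6 observed, against 3 × 12 = 36 with full follow-up. The observed rate ratio is (84 + 6 × 2)/90 = 1.07. With full follow-up and the doubled hazard persisting it is (84 + 36 × 2)/120 = 1.30. Using observed time helps, but it does not remove informative loss.

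**The case against.** The other side has a good deal of substance.

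- A reader might infer that the plan scores early leavers as fall-free and therefore understates falls on TZ. The documents support neither step. Nothing in them assigns leavers a value, and they do not quantify loss by arm.
- Falls before stopping are recordable and count. Section 4.4 names falls among the side effects that can lead to withdrawal, so some high-risk leavers would already be scored as fallers.
- The protocol does provide for later data: 6.2.4, section 8, the final visit requested in 6.2.3 and 4.4, and the 30-day window in 9.3. The window is a softer safeguard than it looks. Adverse events are elicited by a question at visits and calls (10.3.1.3), no contact is scheduled for someone who has left, and 10.3.1.1 exempts outcome-measure results from adverse event recording.
- Differential loss would not be hidden, because drop-out by arm is part of the primary outcome.
- A reader might also infer that the bias could turn an excess of falls on TZ into an apparent deficit. With three leavers at week 2, twice the hazard in leavers, 30% placebo risk and no placebo loss, TZ shows 24.4% against a true 36.3%. That needs the doubled hazard to last ten weeks after drug is stopped. If it ends at stopping, true TZ is 0.7 × 30% + 0.3 × (1 − 0.7^(14/12)) = 31.2%, an excess of 1.2 points. Nothing in the documents supports the persistent case.
- This is a secondary outcome in a 20-person pilot. Power for 50% v 30% is about 14% at a two-sided 5% level, so no test result hangs on it.

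What remains is the contradiction between 6.2.3 and 6.2.4 with section 8, and the absence of a rule in 9.4. None of the points above removes either.

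**Conclusion.** The point holds as a gap in the plan and a possible bias; the documents do not establish that the bias will occur. Falls are analysed as a proportion over everyone randomized without regard to observed time, the sections on follow-up after stopping drug conflict, and no scoring rule is stated. If 6.2.3 governs, a leaver with no recorded fall can be counted as fall-free on partial data. Falls on TZ are then understated relative to placebo only if TZ has more or earlier stops. The protocol's own account of TZ makes that plausible but gives no figures.

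Under the assumed rates in the table, the bias at 30% risk lies between −0.4 and −7.3 points. In an arm of ten the largest of these is 10 × 0.073 = 0.73 of a participant. The scoring rule matters more for any single data set: the example moves from 30% to 60% on the same observations. The effect is on the descriptive estimate. It is worth correcting before unblinding, but it does not undermine the trial.

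**What to change.** 1. **Reconcile 6.2.3 with 6.2.4 and section 8** on data collection, so that the falls question continues at the visits and calls already scheduled (weeks 3, 4, 5, 6, 9 and 12) for participants who have stopped drug and agree to contact. This concerns observation only and leaves the reasons for stopping drug untouched.
2. **In 9.4, replace the bare chi-square for falls.** Report, by arm, participants with at least one fall together with observed person-weeks. Estimate time to first fall (Kaplan-Meier at week 12) or first falls per person-week, as a descriptive estimate with a 95% CI. Counting first falls rather than all falls avoids one repeat faller dominating an arm of ten.
3. **Add a two-row bounds table** in which leavers with no recorded fall are scored first as non-fallers and then as fallers.

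The cost is a few sentences in the protocol and analysis section, plus falls questions at contacts already in the schedule. Intervals will be wide at 10 per arm. The time-based estimates still assume that leaving is unrelated to fall risk, which is why items 1 and 3 are needed alongside item 2.

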Parkinson's disease (PD) is a devastating neurodegenerative disease affecting ~1 million Americans with ~60,000 new diagnoses made annually¹. There are no interventions that slow the inexorable progression of PD. Thus, there is a ***critical need*** to develop novel disease-modifying therapies for PD. We have discovered that activation of phosphoglycerate kinase 1 (Pgk1) can reverse energy deficits that contribute to the pathology of PD. More importantly, we have discovered that terazosin (TZ) can activate Pgk1 through a novel mechanism that is independent of its predicted α -adrenergic receptor antagonism and slow the progression of PD. The procedures outlined in the protocol will allow us to 1) quantify energy deficits in the brains of patients with PD and 2) determine if the administration of TZ can alter energy deficits over a short time period and longer time period. **This study will test the safety and tolerability of TZ in patients with PD as well as test the feasibility of this protocol while providing vital information to guide future clinical trials of TZ in PD.**

Study Title

A FeASibiliTy study of TeraZosin as a disease modifying treatment for PD: FAST TZ-PD

Objectives

Primary objective:

To assess the safety of TZ in patients with PD as well as the feasibility of the study protocol. The active treatment group (TZ 5mg daily) will be compared to a placebo group. The primary outcome measure will be the safety and tolerability of TZ in the select patient population. This will be assessed by comparing the number of participants in each group that experience drug-related adverse drug events as well as assessing the rate of drop out in each group.

Secondary objective:

Orthostatic hypotension is more common in PD², so it is possible that TZ could exacerbate this symptom of PD. To assess the change in blood pressure (systolic and diastolic) from baseline to week 6 and from baseline to week 12.

Exploratory Objective:

[figure not shown]
To quantify ATP levels in 1) red blood cells and 2) in the brain before and after the administration of TZ and after taking TZ for 12 weeks.

Design and Outcomes

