2.3 Risk/Benefit Assessment

As mentioned previously, TZ is associated with an increased risk for orthostatic hypotension (OH). This is especially important in the setting of PD where the prevalence of OH is significantly increased compared to healthy controls. Patients with PD are also more susceptible to falls, which could also be exacerbated by the presence of OH. The results from the Truven database outlined above demonstrated that patients with PD who were using TZ did not have significantly increased prevalence of ICD-9 codes related to falls compared to PD patients who were not using TZ. However, this study will directly assess whether or not the use of TZ in PD significantly increases the occurrence of orthostatic hypotension and related events, such as falls. TZ is associated with additional adverse effects, such as peripheral edema, palpitations, nausea, asthenia, dizziness, headache and somnolence. Despite these risks, the potential benefit that TZ may provide is significant given that there are no currently available treatments to slow the progression of PD.

FAST TZ-PD

Version 2.0

Version date: 11/12/2019

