4.2 Exclusion Criteria

1. Subjects unwilling or unable to give informed consent
2. Secondary parkinsonism (e.g., drug induced)
3. Parkinson-plus syndromes
4. History of brain surgery for PD such as deep brain stimulation
5. No confounding acute or unstable medical, psychiatric, orthopedic condition. Subjects who have hypertension, diabetes mellitus, depression, or other common age-related

FAST TZ-PD

Version 1.8

Version date: 2/7/2019

illness will be included if their disease under control with stable treatment regimen for at least 30 days.

6. Neurogenic orthostatic hypotension defined as symptomatic decrease in BP > 20mmHg systolic or > 10mmHg diastolic and HR increase < 20bpm on supine to sitting or standing.
7. Clinically significant traumatic brain injury or post-traumatic stress disorder
8. Presence of other known medical or psychiatric comorbidity that in the investigator's opinion would compromise participation in the study
9. Presence of dementia per Movement Disorder Society Level I criteria
10. Major depression, bipolar affective disorder, or other mental health disorders that are sufficiently severe to increase adverse event risk or impact neuropathy assessment in the opinion of the responsible site principal investigator.
11. Current suicidal ideation within one year prior to the baseline visit as evidenced by answering "yes" to Questions 4 or 5 on the suicidal ideation portion of the Columbia-Suicide Severity Rating Scale (C-SSRS), Beck Depression score >21, Beck Anxiety score >22.
12. History of exposure to typical or atypical antipsychotics or other dopamine blocking agents within 6 months prior to the baseline visit
13. Use of investigational drugs within 30 days before screening
14. Subjects have to be on a stable regimen of central nervous system acting medications (benzodiazepines, antidepressants, hypnotics) for 30 days prior to the baseline visit
15. Use of doxazosin, alfuzosin, prazosin, or tamsulosin
16. For female participant, pregnancy, or plans for child-bearing during study period
17. Participant is restricted from traveling to and from the study site

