6 CLINICAL AND LABORATORY EVALUATIONS/STUDY PROCEDURES

6.1 Schedule of Activities

Evaluation	Screening (-90 days)	Day 1	2 wks	3 wks	4 wks	5 wks	6 wks	9 wks	12 wks
Written Informed Consent	X								
Inclusion/Exclusion Review	X	X							
Documentation of Disease/Disorder	X	X							
Hoehn & Yahr	X	X	X				X		X
Medical History • Overall Medical History • Medical History of PD	X	X					X		X
Concomitant medication review	X	X	X				X		X
Orthostatics^a	X	X	X				X		X
MDS-UPDRS Motor assessment^b	X	X	X				X		X
Physical examination	X	X					X		X
Randomization^c		X							
Dispense Study Drug^d		X							
Blood Draw		X ^c					X		X
MRI		X ^c							X
Neurological examination	X	X					X		X
Body weight and height	X	X	X				X		X
Vital signs	X	X	X				X		X

Finger Tapping Assessments		X	X				X		X
Behavioral Assessments									

 Columbia Suicide Severity Rating Scale Questionnaire for Compulsive Disorders (C-SSRS) Beck Anxiety Inventory Beck Depression Inventory Parkinson's Disease Questionnaire (PDQ-39) 	X ^e	X	X ^f				X		X
Sleep assessment		X					X		X

 Pittsburgh Sleep Quality Index 									
Recent Falls			X	X	X	X	X	X	X
Cognitive Assessments		X					X		X

 Hopkins Verbal Learning Test (HVLT) Symbol Digit Modalities Test (SDMT) MoCa 									
Auditory/Speech Assessment		X	X				X		X
Pregnancy Test for Women of Child-Bearing potential	X	X	X				X		
Timed Up and Go Assessment		X	X				X		X
Drug Accountability/ Compliance			X	X	X	X	X	X	X
Adverse Event Review			X	X	X	X	X	X	X

a) Participants will lie in the supine position for 5 minutes and have their blood pressure checked. The patient will then sit up for 1 minute and have their blood pressure re-checked. The patient will then stand for 3 minutes and have their blood pressure checked. If the participant has a decrease in the systolic blood pressure by 20 or more mmHg after standing for 3 minutes, or a decline of 10 or more mmHg in the diastolic blood pressure, they will be considered to have orthostatic hypotension.

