6.3.8 Clinical Assessments

- Hoehn & Yahr
 - Collected to measure disease severity as well as progression throughout study
- Orthostatics
 - Collected to measure if participants are having worsening orthostatic hypotension.
 - If orthostatic hypotension is present, this assessment will NOT be able to determine if it is secondary to the study medication or autonomic failure that occurs in PD.
- Physical examination
 - This will be a simple physical exam to measure the general health of the participant independent of their PD
- MDS UPDRS Part 3
 - This portion of the MDS-UPDRS specifically measures motor function. This will only be collected when subjects are in the practically defined "off-period" meaning that they have not taken their PD medications within 6 hours of the assessment
- MDS-UPDRS Part 4
 - This portion of the MDS-UPDRS will use historical and objective information to assess the motor complications of dyskinesia and motor fluctuations including off-state dystonias
- Vital signs/Height & Weight

FAST TZ-PD

Version 2.0

Version date: 11/12/2019

- Participants will have their heart rate, respiratory rate, blood pressure, and core body temperatures measured as well as their height and weight
- Neurological Exam

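### Section 9.4 tests orthostatic hypotension only as a yes/no prevalence at 10 v 10; the measured postural fall has no analysis, and the BP-change outcome has no posture or method

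*Combined protocol and SAP*

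**What the plan says.** Section 9.4 lists, among the secondary outcomes, "Prevalence of orthostatic hypotension between placebo and active group" with chi-square as the method. It names no visit, does not choose between any-visit and single-visit prevalence, and has no baseline term. OH prevalence does not appear in the outcome list of 9.1.2.

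Footnote a of the Schedule of Activities (6.1) has blood pressure taken after 5 minutes supine, 1 minute sitting and 3 minutes standing. The schedule places this at screening, Day 1 and weeks 2, 6 and 12. The readings serve only to classify OH: "If the participant has a decrease in the systolic blood pressure by 20 or more mmHg after standing for 3 minutes", or a diastolic drop of at least 10 mmHg.

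Three places state what the measurements are for:
- Section 6.3.8, on orthostatics: "Collected to measure if participants are having worsening orthostatic hypotension".
- Section 2.3: "this study will directly assess whether or not the use of TZ in PD significantly increases the occurrence of orthostatic hypotension".
- The synopsis, which rests the BP objective on OH being more common in PD: "so it is possible that TZ could exacerbate this symptom of PD. To assess the change in blood pressure (systolic and diastolic".

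The BP outcome is listed in 9.1.2 as "Mean change in systolic and diastolic blood pressure from baseline to 6 weeks and 12 weeks". It is also the secondary objective in 1.2 and is repeated under the primary outcome in 9.1.1. None of these names a posture, and 9.4 gives no method for it. The general rule in 9.4 is intention to treat: "All randomized individuals will be included regardless of their final treatment status".

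**The concern.** The count answers the question in section 2.3 about how often OH occurs. It does not serve two other stated purposes.

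First, worsening is a change from baseline, and a prevalence without a baseline term does not measure change. It also discards how far standing pressure fell: a fall of 19 mmHg and a fall of 0 count the same.

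Second, the BP-change objective is justified by OH risk. If seated or supine pressures were analysed, the result would not bear on that risk, and the plan does not say which posture it means.

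The missing visit matters because OH stops study drug (6.2.3 and section 8). A week-12 prevalence could miss someone whose OH at week 2 resolved after stopping, whereas an any-visit count would not. Baseline matters because section 4.2 item 6 excludes only "Neurogenic orthostatic hypotension defined as symptomatic decrease in BP > 20mmHg systolic or > 10mmHg diastolic and HR increase < 20bpm", while the synopsis excludes OH without that qualification. If symptom-free OH meeting footnote a can be enrolled, the count mixes existing and new cases.

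At stake is a safety conclusion that will probably read as no significant difference in OH, with nothing beside it to show how large a postural effect remains plausible. Posture, visit and baseline would then be chosen after unblinding, on 20 people.

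**Working it through.** **Inputs from the plan.** Ten per arm, 1:1. Section 9.2 bases the sample size on funding. The documents give no alpha, power, SD or OH rate, so there is no stated figure to reproduce. I take two-sided 0.05.

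**1. What the count can show (no SD needed).** For *a* v *b* cases, uncorrected chi-square = 20 × [a(10−b) − b(10−a)]² / [(a+b)(20−a−b) × 100].
- 4 v 0: 20 × 40² / (4 × 16 × 100) = 5.00, p = 0.025.
- 3 v 0: 20 × 30² / (3 × 17 × 100) = 3.53, p = 0.060.
- 4 v 1: 20 × 30² / (5 × 15 × 100) = 2.40, p = 0.12.

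Enumerating all tables, p<0.05 needs at least 4 v 0, 6 v 1, 7 v 2 or 8 v 3. Fisher needs 5 v 0, 7 v 1, 8 v 2 or 9 v 3. Exact chi-square power is 0.14 for true rates of 10% v 30%, and 0.47 for 10% v 50%.

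Newcombe interval for 4 v 1: the Wilson limits are 0.168–0.687 and 0.018–0.404. Lower limit: 0.30 − √(0.232² + 0.304²) = −0.08. Upper limit: 0.30 + √(0.287² + 0.082²) = 0.60.

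**2. Precision of the fall (assumed SDs).** Let B be the between-person SD and W the within-visit SD of the systolic fall, with the mean of the two baseline falls as covariate. Residual variance for the average of three visits is B² + W²/3 − B⁴/(B² + W²/2). For one visit, replace W²/3 by W². The 95% half-width is about 2.11 × √(2/10) × residual SD.
- B = W = 6: averaged, 48 − 24 = 24, half-width 4.6 mmHg; one visit, 72 − 24 = 48, half-width 6.5.
- B = 9, W = 10: averaged, 114.3 − 50.1 = 64.2, half-width 7.6; one visit, 181 − 50.1 = 130.9, half-width 10.8.

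Simulation that also allows for chance baseline imbalance and for stopping at OH gives 4.4–9.3 averaged and 6.6–11.0 at one visit.

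**3. Count against fall under the stop rule (simulation, 20,000 trials per scenario; all inputs assumed).** Systolic mean fall 3, 5 or 6 with B/W of 6/6, 8/8 or 9/10. Diastolic mean −2, 0 or 1 with SDs 4/4, 5/5 or 5/6. Systolic–diastolic correlation 0.5. OH screened out at entry, or not. Terazosin adds 8/4 mmHg in every participant, with 40% of that at week 2, so the averaged effect is 8 × (0.4 + 1 + 1)/3 = 6.4 mmHg.

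| After a first OH reading | Any-visit chi-square power | ANCOVA power, averaged systolic fall |
|---|---|---|
| Stays on drug | 0.15–0.20 | 0.37–0.76 |
| Drug effect lost | 0.15–0.20 | 0.20–0.70 |
| No further readings | 0.15–0.20 | 0.23–0.71 |

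The low end of each ANCOVA range is the largest SD. With B/W of 8/12 (total SD 14.4), no entry screen and the effect lost after OH, the two are about 0.16 and 0.18. With 5/2.5 mmHg, the count has 0.05–0.09; the fall has 0.17–0.39 on drug and 0.11–0.36 with the effect lost.

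The order can reverse. If the same mean 8/4 effect sits in 30% of terazosin participants (8/0.3, about 27 mmHg systolic each) and is lost after OH, then at SD 6/6 the count has about 0.25 and the fall about 0.19.

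**4. Dilution.** When the effect is lost after OH, the averaged intention-to-treat difference drops from 6.4 to 4.1–5.7 mmHg.

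**The case against.** The strongest reply is that this is a 20-person pilot sized on funding, that section 2.3 asks about occurrence, and that 9.4 counts occurrence. On that view a continuous summary is a preference, and its apparent advantage comes from assumed SDs. Under the plan's own rule that OH stops drug, the advantage nearly disappears at large SDs. An average over 2 mg, 5 mg and off-drug readings also pulls a safety signal towards zero, while an any-visit count keeps the on-drug event. Adverse events, dropout and falls give further cover.

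Much of this stands. It is why the count should stay, why by-visit results must sit beside any average, and why no power claim is made. Two things survive it. The text gaps do not depend on any simulation: no visit, no baseline, no analysis of the fall, and no posture or method for BP change. And 9.4 already assigns linear mixed models to compliance and to many exploratory scales, so leaving BP out is not a general choice of simplicity.

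It would be unfair to call BP change wholly undefined. It does name weeks 6 and 12 and a between-arm mean comparison.

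**Conclusion.** The point holds as an analysis gap that should be closed. What is firm is the reading of the text and the 10 v 10 arithmetic: fewer than 4 v 0 cases cannot reach p<0.05, and a 4 v 1 split is compatible with anything from 8 points fewer to 60 points more OH on terazosin. What rests on assumed SDs, effect size and stopping behaviour is any comparison of power.

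A reader might infer three stronger things that the documents do not support:
- *That the fall should replace the count, or is the better test in general.* The documents give no SDs. The advantage shrinks under the stop rule and can reverse when the effect is concentrated in a few people.
- *That the added estimate would choose the next dose.* Only one maintenance dose is studied, and half-widths of about 4 to 9 mmHg stand against an intention-to-treat effect of 4.1–5.7 mmHg in the 8/4 scenario.
- *That the count is known to be contaminated by OH present at entry.* That depends on which eligibility wording governs, which is a separate conflict between the synopsis and 4.2.

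Two other conflicts are also separate: follow-up after stopping drug (6.2.3 against 6.2.4), and the timing of Day 1 assessments (footnote c against 6.2.1).

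**What to change.** In section 9.4:

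1. **Keep the OH count** and define it as OH by footnote a at any post-baseline visit. Report an exact test and a 95% CI for the risk difference. List how many in each arm already had OH at screening or Day 1, but do not cross-classify by visit and baseline status, because the cells would be nearly empty.
2. **Add the between-arm difference in the supine-to-3-minute-standing fall**, systolic and diastolic, from a mixed model or ANCOVA adjusted for the pre-dose baseline fall. Use all randomised participants and all available week 2, 6 and 12 readings, including those after drug stop. Give 95% CIs by visit (week 2 is 2 mg; weeks 6 and 12 are 5 mg) and averaged.
3. **Analyse the 9.1.2 BP change** at weeks 6 and 12 with the same baseline-adjusted model for standing pressure, with supine alongside.

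Cost: wording only, with no new measurements. Item 2 adds 2 × (3 + 1) = 8 estimates; item 3 adds 2 pressures × 2 postures × 2 visits = 8. All should be read as estimates. A Fisher test is stricter than the present chi-square (5 v 0 instead of 4 v 0), so the CI should carry the message. The averaged difference is diluted by 2 mg and off-drug readings, so the by-visit results and the any-visit count must be shown next to it. Readings after drug stop exist only if such participants are actually followed.
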